### **REDCap**

This study will utilize REDCap issued through the Atlanta Veterans Health Care System. Only deidentified data will be entered in REDCap by VA credentialed research personnel to run data analysis.

### **Power Analysis and Sample Size**

For Aim 1, we used preliminary data comparing older active adults to older sedentary adults. Effect size for difference in inferior frontal perfusion for a small sample ( $n=10$ ) was  $d=2.740$ . If this effect size is taken as an estimate of the effect size for change in the Spin group with  $n=44$  and  $\alpha$  FDR-corrected to 0.0261, then power approaches 1.00. A more conservative estimated change in perfusion being half the effect, with the standard deviation remaining constant, would produce an effect size of 1.370. With the same  $n$  and  $\alpha$  as above, the power still approaches 1.00. The required effect size to achieve a power of 0.80 would be  $d=0.5$ , which would seem quite achievable given our preliminary data. Hence, the power should be more than adequate and seems plausible based on what we know. Because we want to maintain sensitivity at this level, the study is powered mainly to this Aim, while power for Aims 2 and 3 is more than adequate. For

example, for Aim 3, with  $\alpha < .05$ , minimum power of 0.80 and 88 subjects, we have the power to detect an increase in  $R^2$  as small as 0.111 in each ROI. We have detected significant correlations between BOLD response in M1 and IFG with smaller sample sizes (n=36 and n=41, respectively). Accounting for much less than 11% of the variance in criterion variables with the predictors would be too little variance to provide information useful for the design of future clinical trials. Hence, we should have the power to detect effects large enough to impact future clinical trials.

For behavioral data, we estimate the effect size for semantic fluency from 2 sources of data using the same treatment we will use for this study. For our lab the effect size for change in the Spin group was  $d=1.804$ , and for the preliminary data from an ongoing study the effect size for change in semantic fluency was  $d=1.410$ . Using the more conservative of the two estimates,  $n=44$  and a FDR corrected  $\alpha=0.0261$ , power approaches 1.00. Again, an effect size of  $d=0.5$  would achieve a power of 0.80, which seems quite achievable given the large effect sizes in two independent samples. Use of the Control in this instance is problematic because of a large negative outlier, yielding a large negative mean (-2.000, indicating a loss of semantic fluency) and a large standard deviation. Even so, these data yield an effect size of  $d=0.886$ , but these data are not stable enough to yield a good estimate of between-group effect size. With  $n=44$  per group and  $\alpha=.05$  (FDR corrected), an effect size of  $d=0.64$  would yield a power of 0.80. Based on the strong effect size for Spin, we believe this is an achievable effect size for a between-group analysis based on what we know about the Spin intervention.

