#### **4. Specific Aims:**

The study will enroll 134 older, sedentary adults. Participants will be pseudorandomized to one of two 12-week intervention conditions: Aerobic Exercise or Stretching.

**Specific Aim 1:** To determine the effect of a 12-week aerobic exercise intervention on changes in cerebral perfusion using arterial spin labeling in older Veterans.

*Hypothesis:* Compared to a non-aerobic intervention Control group, the aerobically trained group will have increased basal perfusion in areas that demonstrate age-related decline and are malleable to aerobic exercise (inferior frontal and motor cortices).

**Specific Aim 2:** To determine the effect of a 12-week aerobic exercise intervention on changes in cerebrovascular reactivity using a hypercapnic CO2 response test in older Veterans.

*Hypothesis:* Following the interventions, aerobically-trained older adults will have increased CVR to CO2 in the inferior frontal and motor cortices when compared to controls.

**Specific Aim 3:** To quantify the impact of cerebrovascular perfusion and cerebrovascular reactivity on the BOLD response during task-based (cognitive executive and motor) fMRI.

*Hypothesis:* Perfusion and CVR will account for a significant portion of variability in the BOLD response during task-based fMRI both before and after the intervention.

*Measures for Specific Aim 3.*

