## **6. Participant selection:**

The study will enroll sedentary older adults and young adults as a comparison group for the MRI scans. Older adult participants will be pseudo-randomized to one of three 12week intervention conditions: Aerobic Exercise, Interval Exercise, or Control. The pre and post evaluations will be conducted over 2 days during a 1-week period. Each day will last no more than 2 hours. The investigators expect a dropout rate of anywhere from 15-20% of participants. To ensure completion of study by 108 participants, as many as 134 subjects may be enrolled.

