## **7. Statistical Analysis:**

### **Statistical Analysis for Specific Aim 1**

Specific Aim 1 is to determine whether there will be a statistically significant difference in the cerebral perfusion data between the two groups (Spin and Control) following the intervention. We will assess the perfusion values jointly using a linear mixed-effects model to determine whether the mean change in perfusion between the groups is significantly different. For the model the fixed effect will be group (Spin vs Control) and the random effect will be time (Pre vs Post). We expect that modeling the outcomes jointly will increase the statistical power. This model will enable us to estimate the

overall effects of time and the interventions, and most importantly, how the effects of the interventions differ with time. Additional analyses will use multiple regressions to describe the effect of participant demographics such as gender, race, age, hypertensive status as well as MoCA score. A false discovery rate (FDR) of  $q = 0.05$  will be calculated and used to correct for multiple tests and effect sizes will be computed.

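### Aim 1 is powered on change within the Spin group, but its test is Spin versus Control: with 44 per arm, 0.80 power needs d of about 0.66, not 0.5

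*Combined protocol and SAP*

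**What the plan says.** Section 4 (Specific Aims) makes the Aim 1 hypothesis comparative: "Compared to a non-aerobic intervention Control group, the aerobically trained group will have increased basal perfusion". Section 7, Statistical Analysis for Specific Aim 1, follows it with a mixed model "to determine whether the mean change in perfusion between the groups is significantly different".

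Power Analysis and Sample Size takes another quantity. It starts from d=2.740, a cross-sectional difference in inferior frontal perfusion between active and sedentary older adults (n=10), and continues: "If this effect size is taken as an estimate of the effect size for change in the Spin group with" n=44 and an FDR-corrected alpha of 0.0261, power is close to 1. It halves the effect to 1.370 with the same result, gives d=0.5 as the effect needed for 0.80 power, and adds that "the study is powered mainly to this Aim, while power for Aims 2 and 3 is more than adequate". Aim 3 is then worked with "minimum power of 0.80 and 88 subjects", which fits two arms of 44.

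The only between-group figure comes in the paragraph on behavioral data. There d=0.5 is repeated for change in Spin. The preliminary Control data are set aside because "these data are not stable enough to yield a good estimate of between-group effect size", and d=0.64 is given for 0.80 power with 44 per group at an alpha of .05, marked as FDR corrected.

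**The concern.** The quantity that was powered is not the quantity that will be tested. A one-group change is judged against its own sampling error. A difference between two groups carries the sampling error of both arms, so at the same n per arm it needs a standardised effect about √2 times as large. A within-Spin d of 0.5 equals a between-group d of 0.5 only if Control has no mean change and the same SD of change, and even then the power differs.

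The Aim 1 paragraph ends by calling power more than adequate for the aim that sets the sample size, so a reader will naturally apply 0.5 to the Aim 1 test. This matters most after a null result: an effect of d=0.5 would seem reliably excluded when the test had little better than an even chance of detecting it. The expected effects do not remove the need for a correct threshold. They come from a cross-sectional contrast in a small sample, as the plan discloses, and not from an observed training change.

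**Working it through.** **Inputs.** From Power Analysis and Sample Size: n=44 in Spin, alpha 0.0261, target power 0.80, stated detectable d=0.5, conservative expected d=1.370, and 88 in total (88/2 = 44 per arm). From section 6 (Participant selection): 108 completers.

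**Assumptions.** The test is two-sided (the plan does not say), the arms are equal, and a t-test on change scores stands in for the mixed model. Here d is in units of the SD of change. Power is P(T > t_crit), where T is noncentral t; the opposite tail is negligible.

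**1. Reproduce the plan's figure (one sample).**
- Noncentrality = d√n, with df = n − 1 = 43 and t_crit = 2.304.
- At d=0.5 it is 0.5 × √44 = 3.317, and power is 0.84.
- Power of 0.80 is reached at d=0.476, which rounds to the printed 0.5.

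**2. The planned comparison (two samples, n per arm).**
- Noncentrality = d√(n/2), with df = 2n − 2 = 86 and t_crit = 2.264.
- At d=0.5 it is 0.5 × √22 = 2.345, and power is 0.53.
- Power of 0.80 is reached at d=0.663.
- Reaching 0.80 at d=0.5 would take about 77 per arm (76 by the normal approximation).

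**3. Sensitivity to n per arm and alpha (two-sided).** Section 6 says "To ensure completion of study by 108 participants, as many as 134 subjects may be enrolled" and, in the same paragraph, "Older adult participants will be pseudo-randomized to one of three 12week intervention conditions". It does not say how the 108 divide, so equal splits into two or three arms are shown as a range.

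| n per arm | Alpha | Power at d=0.5 | d for 0.80 power | Power at d=1.370 |
|---|---|---|---|---|
| 44 (88/2) | 0.0261 | 0.53 | 0.66 | >0.999 |
| 44 (88/2) | 0.05 | 0.64 | 0.60 | >0.999 |
| 54 (108/2) | 0.0261 | 0.63 | 0.60 | >0.999 |
| 36 (108/3) | 0.0261 | 0.44 | 0.74 | >0.999 |

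With 44 per arm, a one-sided test at 0.0261 needs d=0.60. Only a one-sided test at an uncorrected 0.05 comes near the printed value (0.53), and the Aim 1 paragraph does not use that alpha.

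**4. The d=0.64 given for semantic fluency.** With 44 per group and a two-sided test, d=0.64 has power 0.84 at alpha 0.05 and 0.77 at alpha 0.0261. It gives 0.80 at alpha of about 0.034 (0.032 to 0.036, allowing for rounding of d). The plan does not state that value.

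**The case against.** The plan openly labels its figure as change in the Spin group, and for that quantity the arithmetic is right and rounded conservatively. It never claims 0.5 between groups. It also gives a between-group 0.64 for the same group size, and because a standardised effect at given n and alpha does not depend on the outcome, that figure carries over to perfusion and is close to 0.66. An approximate FDR alpha of 0.05(m+1)/(2m) gives 0.0261 for m=22 or 23 tests and 0.0333 for m=3; at 0.0333 the detectable d is 0.642. So 0.64 may be right for its own family of tests. Sidedness is not stated, and the plan expects its joint mixed model to add power. Finally, power at d=1.370 is secure.

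Much of this stands. The fault is a mismatch between the power calculation and the test, not a slip in computing. The value 0.66 depends on its assumptions, and different families of tests may have different FDR-corrected alphas. But the between-group step was taken for fluency and left out for the aim that sets the sample size. The number of tests behind either alpha is not given, so the reconstruction of 0.64 is plausible but cannot be confirmed. The gain from joint modelling is expected but not quantified, and the power text does not use it.

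**Conclusion.** The concern holds. The stated detectable effect for the main aim applies to change within Spin and not to the Spin-versus-Control difference that Aim 1 tests. With 44 per arm and two-sided alpha 0.0261, the planned comparison has power of about 0.53 at d=0.5 and needs d of about 0.66 for 0.80. A one-sided 0.0261 or a two-sided 0.05 gives 0.60. If the 108 completers are split equally, the figure at two-sided 0.0261 is 0.60 for two arms or 0.74 for three.

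These values rest on the t-test proxy and on d measured in SDs of change; covariates or a different variance structure would move them. The trial is not shown to be underpowered for the effect it expects, only less sensitive to moderate effects than the text suggests. It should be fixed.

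**What to change.** In the Aim 1 paragraph of Power Analysis and Sample Size, state the detectable effect for the Spin-versus-Control difference in perfusion change, together with sidedness, alpha, analysed number per arm and method. With 44 per arm, two-sided alpha 0.0261 and a t-test on change scores, that is d of about 0.66 for 0.80 power. If another number per arm will be analysed, restate it for that number (0.60 at 54, 0.74 at 36). Label d=0.5 as change within Spin only, or delete it.

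In the behavioral paragraph, state the alpha that underlies d=0.64. Either use one alpha throughout or say which family of tests each corrected alpha belongs to.

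The cost is wording in two paragraphs and a less favourable stated detectable effect. No participants, visits or analyses are added.

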#### **8. Adverse event reporting:**

In the case of a reportable event, the Principal Investigator will follow the current Atlanta VA Research and Development operating procedure for reporting. This includes notifying the Emory IRB within the appropriate time period of any adverse event occurring.

All study staff will be trained on proper reporting procedures of adverse events (i.e.- contact emergency medical services for immediate medical emergency and later the Principal Investigator, if not present). The PI will notify the IRB and VA SIO of any reportable events.

#### **9. Data and safety monitoring plan (DSMP):**

This is a minimal risk protocol and therefore **data will not be reviewed by a Data Safety Monitoring Board (DSMB) or Data Monitoring Committee (DMC).**

#### **Protection Against Risk**

Several precautions will be made to reduce the risk of exercise-related injuries:

- The exercises are carefully designed with warm-up, stretching and cooling down components to minimize injuries;

- Written instructions highlighting some fundamental guidelines all study participants should do to ensure that they are exercising safely will be provided to all study participants;
- For those individuals who are extremely de-conditioned, frequent rest periods and exercise from a sitting position will be offered at the beginning of the training period;
- Additionally, the pre/post testing carries minimal risks due to the sub-maximal nature of the fitness testing. As per the YMCA protocol, “physician supervision is not necessary with sub-maximal testing in low to moderate risk adults.” (ACSM’s Health Related Physical Assessment Manual, 2007).
- At each exercise session, participants will be questioned about the presence of musculoskeletal symptoms;
- If a participant experiences a significant illness requiring mobility restriction, surgery or hospitalization, the project coordinator will contact the participant’s primary physician, physician assistant, or nurse practitioner for clearance to return to the intervention classes.
- If adverse symptoms develop a 1-week hiatus from the exercise session will be enforced, and during this time the participant will perform static stretching exercises. A slow reintroduction of the exercise program will follow all hiatuses;
- The instructors/evaluators will be instructed to be alert for the emergence of symptoms of angina and shortness of breath. Participants will be instructed to discontinue exercise if there is significant pain, weakness, or joint swelling after exercise.
- We will ensure that that the site has immediate access to a phone and that provision of interventions and evaluations are undertaken in the immediate vicinity of a phone. All trainers and evaluators will also be encouraged to carry cell phones;
- All activities will occur inside an air-conditioned facility because environmental extremes are poorly tolerated;
- Every precaution will be taken to provide fluids, rest and other measures to ensure each participant is comfortable, safe and secure in the testing environment.

Confidentiality of data is maintained by using research identification numbers that uniquely identify each individual. Safeguards are established to ensure the security and privacy of participants’ study records. The information collected from participants in this study has a low potential for abuse, since the data do not address sensitive issues. Nevertheless, appropriate measures are taken to prevent unauthorized use of study information. A research ID number will be used. The research records will be kept in a locked cabinet in the locked office of the PI. The files matching participants' names and demographic information with research ID numbers are kept in a separate locked room and are stored in a locked file that uses a different key from that of all other files. Only study personnel have access to these files. Electronic data will be stored in a password protected file on a secure network. Identifiers might be removed from the identifiable

private information that are collected. After that removal, the information could be used for future research studies. After the study is completed, procedures for long-term storage of VA data will be followed.

FMRI data will be stored in a secure electronic environment in a locked office (6205 A&B) at the Woodruff Memorial Research Building, [name], without identifiers.

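### Staff must watch for angina and breathlessness during training, but no action is attached and no clinician review is required before the participant returns

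*Combined protocol and SAP*

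**What the plan says.** All the relevant rules are bullets in one list, Section 9, Protection Against Risk.

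- **Alert.** "The instructors/evaluators will be instructed to be alert for the emergence of symptoms of angina and shortness of breath". The bullet gives staff nothing further to do about these symptoms.
- **Stop instruction.** The same bullet continues: "Participants will be instructed to discontinue exercise if there is significant pain, weakness, or joint swelling after exercise".
- **Session question.** At each session "participants will be questioned about the presence of musculoskeletal symptoms". No other symptom is listed.
- **Break.** "If adverse symptoms develop a 1-week hiatus from the exercise session will be enforced", with static stretching in the meantime. Then: "A slow reintroduction of the exercise program will follow all hiatuses".
- **Clearance.** "If a participant experiences a significant illness requiring mobility restriction, surgery or hospitalization", the project coordinator seeks clearance from the participant's primary physician, physician assistant or nurse practitioner before classes resume.
- **Written guidance.** The plan promises "Written instructions highlighting some fundamental guidelines all study participants should do to ensure that they are exercising safely". Its content is not shown.

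**The concern.** The plan singles out two cardiac warning signs and then does not say how to act on them. It already has a route that leads to a clinician, but neither sign is among that route's triggers. A participant with new exertional chest discomfort, or breathlessness out of keeping with the effort, could therefore go back to training without medical review and without any departure from the protocol.

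The population makes this worth settling. Older participants are sedentary, the age range runs to 80, and controlled diabetes is allowed (Section 6, Inclusion/Exclusion Criteria). The Risks/Discomforts section says that screening includes no ECG. It also says that cardiac events in exercise are rare but tend to occur at high intensity, and the aerobic arm is designed to progress in intensity. At stake is the safety of a few participants. No endpoint, sample size or analysis is affected.

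**Working it through.** The plan states no figure on this point, so the check is a reading of its rules, followed by simple arithmetic on missed sessions.

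**Step 1. Does the break rule cover angina?** The text does not say, so take both readings.

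- *Broad reading: any adverse symptom.* Angina leads to one week of stretching and then a gradual restart. No clinician contact is part of the rule.
- *Narrow reading: musculoskeletal complaints.* The list is introduced as precautions against exercise-related injury, and stretching suits that purpose. Angina then has no written return rule at all.

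Under both readings, clinician review before return is not required.

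**Step 2. Does another provision supply the missing step?**

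| Provision | Where | What it covers | Condition for return? |
|---|---|---|---|
| Clearance bullet | Protection Against Risk | Significant illness with restricted mobility, surgery or admission | Yes, but angina or breathlessness alone is not a trigger |
| Stop instruction | Protection Against Risk | Significant pain, weakness or joint swelling; chest pain could be read in, breathlessness is not named | No |
| Medical approval | Inclusion/Exclusion Criteria | Before any study procedure | No; it predates a symptom that emerges in training |
| Session monitoring, including remote | Interventions | Observation, by a fitness specialist with CPR certification in the aerobic arm | No |
| CPR, defibrillator, emergency services | Exercise Lab Space; Section 8 | Emergencies | No |
| Adverse event reporting | Section 8 | Notice to the Principal Investigator, the IRB and the VA official named there | No |
| Symptom limits on treadmill tests; ECG on maximal tests | Physical Function | Testing before and after the intervention | No; it does not cover weeks of training |

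No provision requires clinician review before training resumes after non-emergency angina or unusual breathlessness.

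**Step 3. How quickly could such a participant reach high intensity?** The aerobic arm starts at 50% and rises by 5% a week, as tolerated, to 90% (Interventions). The start is expressed on heart rate reserve and the ceiling on maximal heart rate, so this is only a nominal count: (90 − 50) / 5 = 8 increases, which puts the ceiling at week 9 of 12 at the earliest. A 1-week break moves that to week 10 or later, and a slow restart later still. The stretching arm is kept below the aerobic zone, so the high-intensity concern does not apply there.

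**Step 4. What would clearance cost an affected aerobic participant?** Scheduled sessions: 3 per week × 12 weeks = 36. The documents give no clearance time; 1 to 3 weeks is assumed.

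| Time away | Sessions missed | Share of 36 | Beyond the existing 1-week break |
|---|---|---|---|
| 1 week | 3 | 8.3% | 0 |
| 2 weeks | 6 | 16.7% | 3 |
| 3 weeks | 9 | 25.0% | 6 |

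These figures price the remedy. They do not measure harm, which cannot be estimated without a symptom rate.

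**The case against.** The strongest reply is that silence in this list is weak evidence about practice. New angina during a session may well be treated as an emergency, since the plan does not define where an emergency begins. If it led to admission or to a significant illness restricting mobility, the clearance bullet would already apply. Section 8 refers to a local operating procedure that is not shown, and the written exercise guidance may cover chest symptoms. A sensible trainer or investigator would probably refer such a participant anyway.

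Much of this stands. It narrows the affected group to participants whose symptoms trigger neither the emergency route nor the clearance route, and it is why no number can be put on them. It does not close the gap, because nothing in the protocol requires the referral.

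Two stronger readings are tempting and should be resisted. A reader might infer that the plan replaces medical review of angina with a fixed seven-day wait. The text never links angina to the break, and nothing says that the break displaces or forbids review. A reader might also picture a participant back near 90% of maximal heart rate after one week. The plan requires a slow restart and progression only as tolerated, so peak intensity would come later.

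**Conclusion.** The concern holds as an unspecified action: two cardiac warning signs are named, no response is attached to them, and on either reading of the break rule no clinician review is required before return to training. The conclusion rests on the text of this document alone and assumes that no unseen procedure fills the gap.

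Existing safeguards lower the risk. The number affected is unknown and, given that the plan describes cardiac emergencies in exercise as rare, probably small. The change should be made because it is cheap and bears on participant safety. Confidence is medium.

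**What to change.** Make two wording changes in Protection Against Risk.

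1. Extend the question asked at each session, on site and remotely, to chest discomfort and to shortness of breath that is out of proportion to effort or does not settle with rest.
2. Add new angina, or breathlessness of that kind, to the triggers of the existing clearance bullet. Exercise stops, the project coordinator contacts the participant's clinician, and training resumes only with that clinician's clearance.

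Keep the 1-week break for other symptoms and emergency services for emergencies.

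The cost is a short addition to a question already asked and, for each affected participant, one contact through a pathway that already exists. No new staff or procedure is needed. There are two downsides. Fitness staff must judge whether breathlessness is unusual during hard cycling, so some calls will prove needless; limiting the wording to disproportionate or persistent breathlessness keeps these down. And if clearance takes longer than a week, the participant misses more training than under the present break.
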